## **B. INNOVATION**

The proposed study will test truly novel hypotheses using innovative methodology. Specifically, it will build on our previous SCOR work investigating sex and gender differences in the stress-relapse connection, while expanding the focus to opioid dependence, a problem of epidemic proportions in the United States. Several studies suggest alpha-2 agonists may be useful in reducing stress-induced craving and relapse in OUDs and studies in cocaine and nicotine dependence suggest that women may be more responsive to these agents as compared to men. However, to our knowledge, there are no previous or ongoing studies investigating gender differences in the impact of alpha-2 agonists in decreasing stress-induced craving or relapse in OUDs. In addition, we will use a novel alpha-2 agent, lofexidine. While lofexidine has been approved for use in England,

it is now being evaluated by the FDA for use in the United States. Studies suggest that lofexidine is better tolerated than clonidine, the alpha-2 agent most commonly used in the United States for opioid detoxification (Gowing et al., 2009). We will utilize a novel dual-level approach by examining the impact of lofexidine on stress and drug cues presented in a laboratory paradigm and on ambient stress, craving and stress cues occurring over the course of a clinical trial. In the latter case, we will use innovative mobile technology to allow for assessment of craving, stress and stress-cue reactivity in the "day to day" natural environment before, during and after treatment in individuals with OUD. We will also assess medication compliance using an innovative video capture procedure. These approaches represent a highly innovative "next step" in the development of personalized, gender-specific treatment for individuals with OUD.

#### C. APPROACH

[figure not shown]

**C.1.b.** Experience with Recruitment, Retention, and Assessment OUDs. [name] has been conducting clinical trials in close connection with local treatment programs over the past 20 years as part of the NIDA-funded clinical trials network (DA013727). The Charleston Center is a public treatment program located 1 block from the MUSC campus. In 2017, Charleston Center treated 356 men and 224 women with primary OUDs. In 2017, the MUSC addiction treatment service treated over 250 patients with OUDs, including approximately 100 individuals on buprenorphine, the target population for this proposal. [name] and colleagues recruited 126 men and women with OUDs from these settings over a two-year period. A subset of these individuals participated in a human laboratory study similar to the proposed project (described below). In addition, this team is currently leading a multi-pronged statewide effort focused on the opioid epidemic which includes a component focused on providing buprenorphine and rapid access to treatment for OUD patients presenting in emergency rooms (ERs). In the MUSC ER, they have identified 56 individuals with OUD in the last 6 months and facilitated treatment at the Charleston Center and MUSC addiction treatment services. Shoreline Behavioral Health in Conway, SC works closes with DAODAS to provide medication-assisted treatment to residents of Horry County. With these multiple recruitment sites, we anticipate no difficulties meeting recruitment goals for the proposed study.

**C.1.c.** Stress Induction Procedures and Neuroendocrine/Physiologic Measurement. [name] has conducted a number of human laboratory studies involving stress induction and drug cue exposure in alcohol, cocaine and nicotine dependence ([name] et al., 2009; Moran et al., 2014; Hartwell et al., 2011; [name] et al., 2006). Of direct relevance, [name] and colleagues completed a pilot study involving a human laboratory stress task in 39 (N=19 women; 20 men) individuals with OUD. Subjects were randomly assigned to either the Trier Social Stress Test (TSST; n=19) or no-stress control (no stress; n=20) followed by opioid cue exposure. Distress tolerance, Inventory of Drug Taking Situations and Time-line Follow-back were completed at baseline. Self-reported visual analog scale ratings of stress and craving, as well as heart rate and salivary cortisol were assessed immediately before and at multiple time points for 60 minutes following the TSST/drug cue exposure. Individuals were followed for one month after the laboratory session to assess opioid use (Time-line Follow-Back) and daily stress. Significant group (TSST vs. no stress) differences emerged in self-reported stress [F(1,35)=41.77, p<.001], anger [F(1,35)=13.00, p<.001], sadness [F(1,35)=4.78, p<.05], cortisol and heart rate

(HR) [F(1,35)=5.28, p<.05], with the TSST group exhibiting more reactivity. Women demonstrated significantly greater self-reported stress [F(1,35)=11.24, p<.01], (Figure 1); however, they exhibited significantly less cortisol response following the TSST as compared to men. Data (Figure 2) are shown as log 10 transformed model-

[figure not shown]

Figure 1: Stress Response

Figure 2: Cortisol Response

based means and standard errors adjusted for baseline cortisol. Of interest, women also exhibited a significantly protracted HR response following the TSST compared to men; it had not returned to baseline by the end of the

[figure not shown]

Figure 3: Heart Rate Response

1 hour follow-up period (Figure 3) suggesting greater noradrenergic stimulation in women. This finding is similar to the gender-specific pattern of response seen in cocaine-dependent individuals in an earlier SCOR study ([name] et al., 2009). Women in this study reported significantly more daily hassles and used opioids on a higher percentage of days in the one-month follow-up period as compared to men (Table 1). In addition, lower distress tolerance, measured at baseline, was significantly associated with a higher percentage of opioid use days for women (b=17.01, p=.013), but not for men. In summary, these data suggest that OUD women demonstrate greater subjective and noradrenergic stress response than OUD men. The pattern of low cortisol and high subjective response to stress exhibited by women in

this study has been associated with higher relapse in studies in cocaine dependence (Back et al., 2010). Furthermore, women reported lower distress tolerance, higher experience of daily hassles and a robust relationship between low distress tolerance and drug use. Taken

together, these preliminary findings suggest that an intervention targeting stress vulnerability, particularly through blockade of noradrenergic activation, may be particularly effective in relapse

prevention for opioid-dependent women.

[figure not shown]
C.1.d. Experience with Ambulatory Assessments. During the last funding period, the MUSC SCOR research group developed ambulatory assessment tools to assess stress

| TABLE 1: MONTH AFTER TESTING         |            |              |           |  |  |
|--------------------------------------|------------|--------------|-----------|--|--|
|                                      | Men (n=21) | Women (n=18) | Stats     |  |  |
| % days using                         | 30.4       | 55.3         | p = 0.107 |  |  |
| Daily Hassles Score                  |            |              |           |  |  |
| One Week 46.3 105.4 p = 0.018 |            |              |           |  |  |
| One Month                            | 41.6       | 87.5         | p = 0.058 |  |  |

reactivity and drug craving, collect data on drug use and withdrawal symptoms, validate abstinence, and measure/encourage medication adherence. The Cue Reactivity Ecological Momentary Assessment (CREMA) paradigm was modified to assess cue- and stress-related nicotine craving (Wray et al., 2015). Over 80% of CREMA sessions were successfully completed (Tomko et al., 2017), supporting the feasibility of remote collection of this type of data. We also capitalized on the capabilities of the REDCap data system to remotely collect self-report of drug use and video confirmation of medication adherence (Tomko et al., in press). In a smoking cessation trial, there was high compliance with video (73.8%) and self-report (74.8%) completion. All

participants agreed that the surveys and videos were easy to use, and the majority of participants preferred the REDCap assessments to traditional, paper measures. In an ongoing pharmacotherapy trial for cannabis use disorder (UG3DA04323), we have observed high compliance with video uploads for medication adherence, with a median of 80% of medication doses verified.

- **C.2.** Research Design and Methods. This project is a double-blind, placebo-controlled trial to assess gender differences in the impact of lofexidine, an alpha-2 agonist, on stress-related opioid craving in men and women with OUD on stable buprenorphine or methadone maintenance. Following this period, participants will be randomized to receive either lofexidine or placebo for a 5-week period during which cue reactivity ecological momentary assessment (CREMA) will be used to assess stress levels, craving and drug use and video confirmation of medication adherence will be employed. Naturalistically collected stress and drug cue reactivity data will be complemented by administration of a validated laboratory stress (the Trier Social Stress Task) and drug cue exposure procedure at the end of the 5-week treatment period while participants are still taking study medications. A schematic of study procedures is shown below.
- **C.2.a. Participants.** A total of 136 participants (68 men and 68 women) with OUD who have been on a stable dose of buprenorphine or methadone for at least 2 weeks, aged 18 to 65 years of age, will be recruited over a 54-

month period. Additional inclusion criteria are consent to random assignment, ability to read and provide informed consent and willingness to remain abstinent from illicit opioids during the 1-week baseline assessment period. Contingency management procedures (described below) will be used to facilitate the maintenance of abstinence during this period. Exclusion criteria are women who are pregnant, nursing, or planning to become pregnant during the course of the study; having a history of or current major psychiatric or medical disorder; hypotension or QTc prolongation on EKG; and meeting criteria for moderate or severe use disorder for another substance with the exception of nicotine. A detailed list of inclusion/exclusion criteria can be found below.

**C.2.b. Recruitment.** MUSC staff will recruit participants from the Charleston Center,, MUSC and community addiction treatment programs, Shoreline Behavioral Health, and through media advertisements As noted in C.1.b., we have a long and successful track record of recruiting from these programs for clinical trials, and the numbers of patients on buprenorphine or methadone maintenance at both sites are more than adequate for recruitment of the required four participants per month to meet the study timeline.

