A.2. Gender Differences in Substance Use Disorders (SUDs). There is growing recognition that biological and psychosocial differences between men and women influence the prevalence, presentation, comorbidity and treatment of SUDs. For example, women tend to use smaller amounts of drugs or alcohol for a shorter amount of time before seeking treatment, a phenomenon known as "telescoping" ([name] and Randal, 2007). A similar trend is seen in OUDs; an analysis of data from a multisite clinical trial demonstrated that women progressed to opioid dependence more quickly and experienced more craving as compared to men (Back et al., 2011). Women with SUDs are also more likely to have comorbid depression and anxiety disorders ([name] et al., 1993; [name] and Randall, 1999) and are more likely to attribute use and relapse to negative emotional states and interpersonal conflict (Connors et al., 1998; Back et al., 2011) as compared to men. There is also evidence of gender differences in neurocognitive and brain responses in drug-dependent individuals. An fMRI study examining gender differences in neural correlates of stress- and drug cue exposure found greater corticostriatal-limbic reactivity in cocaine-dependent women during stress exposure, but higher reactivity in these regions during drug cue exposure in cocaine-dependent men suggesting greater neural stress sensitization in women (Potenza et al., 2012). Another study found psychological and emotional distress were identified as risk factors for hazardous prescription opioid use among women, but not men (Back et al., 2011).

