Statistics and Data Analysis (complete statistical/data analysis plan in Biostatistics Resource Core): Aim 1: Using a human laboratory paradigm, determine the impact of lofexidine on stress and drug cueinduced craving in women and men with OUDs: The primary study outcome of interest in Aim 1 is the differential craving, stress and anxiety response to a human laboratory paradigms containing both a stressor (TSST) and an opioid specific cue between participants randomized to lofexidine and placebo in addition to buprenorphine/methadone maintenance. Hypothesis 1: Lofexidine will attenuate drug craving and subjective stress response to a stress task in opioid-dependent individuals compared to individuals receiving placebo. Hypothesis 2: Lofexidine will attenuate drug craving and subjective stress response to a drug-related cue in opioid-dependent individuals. Hypothesis 3: The ameliorative effects of lofexidine on stress and cue-reactivity will be more pronounced in females than male subjects. To assess the hypothesis that lofexidine will attenuate drug craving and subjective stress response to the stressor and the opioid-related cue task, multilevel longitudinal GLMMs will be developed using all post-stressor and post-cue data. Initial models will control for study design aspects such as order (stressor or cue first), treatment assignment, and baseline craving and stress (task level). Covariate adjusted models will additionally include baseline characteristics determined to be correlated with study outcomes or those determined to be significant effect modifiers. To examine the differential effects of lofexidine on stress and cue-reactivity across female and male subjects, the models will have additional parameters added to include an indicator of participant gender and the interaction between gender and randomized treatment assignment. Relevant interactions will be assessed in all models. Least square means and associated standard errors will be assessed to compare craving and subjective stress response between treatment assignments at all time points.

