Aim 2: To evaluate the impact of lofexidine on opioid craving and subjective experience of daily stressors in men and women with OUDs: The primary measures of interest for Aim 2 are craving and stress ratings in response to stress-related cues using *Cue Reactivity Ecological Momentary Assessment* (CREMA) as well as subjective experiences of daily life stressors Hypothesis 1: Lofexidine will decrease craving and decrease the subjective experience of daily stressors in opioid-dependent men and women. Exploratory Hypothesis 2: Lofexidine will be more efficacious in decreasing stress-related craving in opioid-dependent women as compared to men. To assess this hypothesis a multilevel generalized linear mixed effects models with repeated measures (GLMMs) will be developed using CREMA session response data from the 5-week period during study medication administration. Pre-cue stress and craving rating will be centered and used as a time varying covariate in all analysis. Additionally, CREMA cue response data during the 7 day baseline assessment period will be used as a time naïve covariate in all analyses. Least squares means and associated standard errors will be used for post-hoc comparisons of craving and stress response between women and men over time. Models developed to address hypothesis 2 will be utilized to examine the impact of gender on opioid use and stress-related craving during study treatment. All other relevant interactions will be assessed in all models.

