## Power and Sample Size (complete sample size justification available in Biostatistics Resource Core):

The current study is powered on the primary Aims 1 and 2. In the proposed study, response to a laboratory stressor, CREMA cue response and daily use data will be tested using GLMMs (assuming a Gaussian distribution) and the study will be powered to sufficiently address the least of the study treatment effect sizes determined to be clinically meaningful for the study hypothesis. Aim 1: Sinha and colleagues (Sinha, et al 2007), in a small pilot sample, demonstrated that lofexiding in combination with naltrexone attenuated craving and anger in response to laboratory drug and stress cues as compared to naltrexone alone. Results indicate a larger change in opioid craving scores in response to drug-related and stress cues occurs in placebo participants than lofexidine treated participants [Drug related cue response  $\Delta$ =2.2; SDP=2.6; between group Cohen's d=0.85, p<0.05 and stress cues response  $\Delta$ =2.1; SDP=2.4; between group Cohen's d=0.88, p<0.05]. Moreover, Fox and colleagues (2014) conducted a trial of quanfacine in cocaine-dependent individuals and noted stress and craving response to stress and drug-related imagery. They noted significant gender differences across treatment assignment for craving and stress response to drug-related imagery [Craving  $\Delta$ =3.0; SDP=3.8; Treatment x Sex Intx Cohen's d=0.79, p<0.05; Negative Emotion  $\Delta=3.0$ ; SDP=2.9; Treatment x Sex Intx Cohen's d=1.0, p<0.05]. Sample sizes in both the Sinha and Fox studies were somewhat small. Smaller but still clinically relevant effect sizes in an adequately powered study are anticipated. Therefore, a 20% reduction in craving and stress response from the previous studies is anticipated in the current design (Cohen's d=0.64 for the sex x treatment interaction on craving response). Aim 2: Kowalczyk and colleagues (2015), showed that daily life craving reports as measured by EMA were significantly reduced in opioid using participants randomized to clonidine as compared to placebo [6.3% (95% CI=5.6-7.1) vs. 11.8% (10.9-13.0); between group Cohen's *d*=1.6]. To assess the least of the differences anticipated in project 2, a sample size of 39 participants randomized to each female and males across active lofexidine and placebo groups would provide 80% power with a type 1 error rate of 5% to detect the treatment x sex interaction in craving and stress response to laboratory drug based cues (total n=156; 78 per group). We anticipate 25% attrition between randomization and the end of the 5-week active treatment period. Thus, inflating the necessary sample size to 68 participants randomized per treatment group with a total of n=136 randomized participants will provide adequate power.

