## 1. Summary of the Protocol.

This application proposes to investigate the effects of lofexidine on stress-induced craving and relapse. The primary outcome of interest is stress reactivity. Inclusion/exclusion criteria are outlined above. Power calculations and sample sizes are in the Data Analysis Plan section above.

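### The plan says it is powered on Aims 1 and 2, but gives no treatment-by-sex effect or power for the stress task, and at 102 evaluable participants neither gender interaction has the stated 80% power at the planning effect

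*Combined protocol and SAP*

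**What the plan says.** Section C.2 (Research Design and Methods) gives the purpose as "to assess gender differences in the impact of lofexidine, an alpha-2 agonist, on stress-related opioid craving in men and women with OUD". The Summary of the Protocol in the data safety and monitoring plan says: "The primary outcome of interest is stress reactivity".

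In C.2.d, Aim 1 covers both laboratory tasks. Its Hypothesis 3 reads "The ameliorative effects of lofexidine on stress and cue-reactivity will be more pronounced in females than male subjects", so it contains one treatment-by-sex interaction for the TSST and one for the opioid imagery. The corresponding Aim 2 statement is labelled exploratory: "Exploratory Hypothesis 2: Lofexidine will be more efficacious in decreasing stress-related craving in opioid-dependent women as compared to men".

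The Power and Sample Size paragraph says the study is powered on primary Aims 1 and 2, and that it is sized on the smallest of the clinically meaningful treatment effects. The only test given a power figure (80% power, 5% type 1 error, 39 per sex-by-treatment cell, 156 in total) is the one "to detect the treatment x sex interaction in craving and stress response to laboratory drug based cues". The planning value, d = 0.64, is a 20% cut from an interaction effect of 0.79 in a guanfacine study in cocaine dependence. The paragraph says that study used both stress and drug imagery, but describes the interaction result this way: "They noted significant gender differences across treatment assignment for craving and stress response to drug-related imagery". The paragraph then allows for 25% attrition and arrives at 136 randomised, which it calls adequate.

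**The concern.** Sizing on the smallest effect protects every hypothesis whose effect is in the set compared. The set here holds two treatment-by-sex interactions (0.79 for craving, 1.0 for negative emotion), both for drug imagery. Its stress-cue entry, 0.88, is a lofexidine-versus-placebo main effect with no sex component. The Aim 2 entry, 1.6, is also a between-group effect. No treatment-by-sex effect for a stressor enters the comparison, so the argument says nothing about the TSST interaction, although stress is what Section C.2 and the monitoring plan put first.

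Two misreadings become possible. A non-significant TSST interaction could be taken as evidence of no gender difference from a trial described as powered for it. A significant drug-cue interaction could be offered as the answer to the stress question, because Hypothesis 3 names both without separating them.

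**Working it through.** **Inputs.** From Power and Sample Size: d = 0.64; 5% type 1 error; 80% power; 39 per cell (156 in total); 25% attrition; 136 randomised. Assumed here: a two-sided test (sidedness is not stated), equal cells, and equal attrition across cells.

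**Smallest effect on the plan's list, after the 20% cut.**
- Drug-imagery interactions: 0.79 × 0.8 = 0.632 (given as 0.64) and 1.0 × 0.8 = 0.80.
- Main effects: 0.85 × 0.8 = 0.68 (drug cue), 0.88 × 0.8 = 0.704 (stress cue) and 1.6 × 0.8 = 1.28 (daily craving).

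The smallest is indeed 0.632, but no item is a stress-task interaction.

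**Reproducing 39 per cell.** Two-group formula: n = 2(1.960 + 0.842)² / 0.64² = 38.3, so 39. This matches, with power 80.7% by the normal approximation and 79.7% by t.

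If d is instead a difference of differences divided by the SD, its variance is 4/n in SD units. Then n = 4(1.960 + 0.842)² / 0.64² = 76.7, so 77 per cell. Coding the interaction as half that difference gives 20. Only the two-group formula returns 39.

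**Number available.** 136 × 0.75 = 102, and 102 / 4 = 25.5 per cell. Keeping 156 after 25% attrition would take 156 / 0.75 = 208 randomised.

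**Power at 25.5 per cell.** The documents give no stress-task interaction effect, so d is a range of assumptions.
- Difference of differences: SE = √(4/25.5) = 0.396, t-test with 102 − 4 = 98 df. At d = 0.64 the ratio is 0.64 / 0.396 = 1.62.
- Plan's two-group formula: SE = √(2/25.5) = 0.280, normal approximation. At d = 0.64 the ratio is 0.64 / 0.280 = 2.29, and power is Φ(2.29 − 1.96) = 63%.

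| Assumed d | Difference of differences | Plan's two-group formula |
|---|---|---|
| 0.40 | 17% | 30% |
| 0.50 | 24% | 43% |
| 0.64 | 36% | 63% |
| d needed for 80% power | 1.12 | 0.78 |

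**Same calculation at the full 39 per cell, d = 0.64.** Two-group formula 81% (80% detectable 0.63); difference of differences about 52% (80% detectable 0.90).

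Nothing in these formulas depends on which task is analysed. The table applies equally to the TSST and to the drug cue at the same d.

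**The case against.** The strongest reply is that the same participants do both tasks, in counterbalanced order, under the same type of model. At an equal standardised effect the TSST interaction therefore has exactly the power of the drug-cue interaction. That stands. What is missing is any stated reason to expect at least 0.64 for the stress task.

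Drug-cue reactivity is also a named part of Aim 1, so the powered test is a legitimate one. A reader might infer that the trial is sized on the wrong hypothesis; the documents do not support that.

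A reader might also infer from Section A.2 that the stress interaction should be smaller, because the imaging study cited there found greater reactivity in women under stress "but higher reactivity in these regions during drug cue exposure in cocaine-dependent men suggesting greater neural stress sensitization in women". That result is brain reactivity in cocaine dependence, not a treatment-by-sex effect on craving in opioid use disorder. Its direction gives no reason to expect a smaller TSST interaction. Section A.4 cites alpha-2 agonist studies with effects in women and not in men, one of them following stress, and the pilot in C.1.c found greater self-reported stress in women. None of these supplies an effect size for the interaction.

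The calculation uses a single standardised response per person, whereas C.2.d plans repeated post-task measurements with baseline adjustment, which may reduce the variance. The documents give no correlations from which to credit a gain. To restore 80% power at 0.64 with 25.5 per cell, the variance would have to fall by a factor of about 39 / 25.5 = 1.5 on the two-group formula, or 77 / 25.5 = 3.0 as a difference of differences.

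Finally, the full sample size justification is said to sit in the Biostatistics Resource Core, which is not part of these documents. A stress-task value may exist there.

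**Conclusion.** The point holds in this form: the plan does not show that it is powered for the TSST part of Aim 1 Hypothesis 3, and the general claim to be powered on Aims 1 and 2 should not stand for the gender interactions. At about 25.5 per cell, power at the plan's own d of 0.64 is about 36% as a difference of differences or 63% on the plan's formula. Below 0.64 it is lower on both scales.

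The low power is not peculiar to the stress task. It comes from having 102 evaluable participants where the plan's own calculation asks for 156 and, on the difference-of-differences scale, from using a two-group formula for an interaction. Both bear equally on the drug-cue interaction, so 80% power cannot be claimed for that test at 136 randomised either. A reader might infer that the stress interaction is worse served than the drug-cue interaction; that would follow only if its effect were smaller, which the documents do not say.

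The figures rest on a two-sided 5% test, equal cells, 25% attrition and no credit for repeated measures. The size of the stress-task interaction is unknown from the documents, so its power can only be given as a range.

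**What to change.** In Power and Sample Size:
- Withdraw, for the gender interactions, the general statements that the study is powered on Aims 1 and 2 and that 136 is adequate.
- State the power and the 80% detectable difference at 102 evaluable for both the TSST and the drug-cue treatment-by-sex interactions, over a range of d that includes 0.64. Say whether d is a difference of differences.
- Label the stress-task effect as an assumption, or quote it from the Biostatistics Resource Core if it is there.

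In the Aim 1 paragraph of C.2.d, report the two interactions separately, each with a confidence interval, so that a drug-cue result is not offered as the answer to the stress question and a non-significant TSST interaction is not read as equal effect. Which of the two ranks first is for the investigators to state; the documents do not dictate it.

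The cost is wording in two paragraphs and a less favourable stated power. It needs no extra participants or procedures.
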